9.3 POPULATIONS FOR ANALYSES

The population for Primary Endpoint 1 will include all patients who are approached for enrollment in the trial. Primary Endpoints 2 and 3 will be analyzed in an intention-to-treat population that includes all patients who are randomized. The secondary endpoints will also be analyzed in the intention-to-treat population of all patients who are randomized.

9.4 STATISTICAL ANALYSES

9.4.1 GENERAL APPROACH

For descriptive statistics, categorical data will be presented using frequency counts and percentages, normally distributed continuous data will be presented using means and standard deviations, and non-normally distributed continuous data will be presented using medians and interquartile ranges.

Normality will be assessed using visual analysis of histograms and using the Kolmogorov-Smirnov test. All inferential tests will be two-tailed, and p-values < 0.05 will be considered statistically significant.

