6.3 MEASURES TO MINIMIZE BIAS: RANDOMIZATION AND BLINDING

Randomization will occur postoperatively at the time of study medication preparation. Patients will be randomized in a 1:1 ratio to ketamine or normal saline placebo. Randomization will occur in blocks of 4. The randomization scheme will be held by the Investigational Drug Service.

Patients, research team members, and clinical staff (nurses, physicians) will be blinded to treatment allocation. To facilitate blinding, study medication for both the ketamine group and the control group will be delivered in 100 mL bags with identical appearance except for a unique study identifier.

Intentional unblinding of the clinical staff may occur in the case of serious adverse events if the attending physician feels knowledge of the treatment allocation will impact clinical decision making. The principal investigator will be notified of all instances of intentional unblinding.

Inadvertent unblinding may occur if the patient experiences side effects such as nystagmus, hallucinations, sedation, or hypertension/tachycardia. To detect inadvertent unblinding of the patient, we will ask the patient during the final study visit if they believe they received ketamine or placebo. To minimize the effects of inadvertent unblinding on study results, endpoints will be measured by study staff who were not present during the study medication infusion.

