9 STATISTICAL CONSIDERATIONS

9.1 STATISTICAL HYPOTHESES

The primary endpoints of this trial will be descriptive outcomes measuring feasibility rather than hypothesis-driven efficacy outcomes. The primary endpoints will include

- Primary Endpoint 1: Fraction of approached patients who enroll in the trial
- Primary Endpoint 2: Fraction of planned study medication infusions that are completed
- Primary Endpoint 3: Fraction of participants with MADRS scores available at all specified time points

The secondary endpoints of this trial will be efficacy outcomes, designed to test the following hypotheses with two-sided superiority comparisons. This feasibility trial is intended to provide estimates of effect sizes, but it will not be powered to test these hypotheses.

- Secondary Endpoint 1: Change in MADRS score between the preoperative assessment and post-infusion day 4
 - Null Hypothesis: The change in MADRS score will be the same in the ketamine group and in the control group.
 - Alternative Hypothesis: The change in MADRS score will be smaller in the ketamine group than in the control group.
- Secondary Endpoint 1: Delta sleep ratio on EEG obtained on the second night following the study medication infusion
 - Null Hypothesis: There will be no difference in delta sleep ratio between the ketamine group and the control group.
 - Alternative Hypothesis: The delta sleep ratio will be greater in the ketamine group compared to the control group.

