9.2 SAMPLE SIZE DETERMINATION

The sample size of 32 has been selected to allow the primary descriptive endpoints to be measured with acceptable levels of precision:

- Primary Endpoint 1: Fraction of approached patients who enroll in the trial

- Conservatively assuming that 25% of approached patients will enroll, then $n = 32$ patients will allow this proportion to be measured with a 95% confidence interval width of $\pm 15\%$:

$$95\%CI = \pm 1.96 \sqrt{\frac{p(1-p)}{n}} = \pm 1.96 \sqrt{\frac{(0.25)(0.75)}{32}} = \pm 0.15$$

- Primary Endpoint 2: Fraction of planned study medication infusions that are completed
 - If we assume that 90% of planned infusions are completed, then $n = 32$ patients will allow this proportion to be measured with a 95% confidence interval width of $\pm 10\%$:

$$95\%CI = \pm 1.96 \sqrt{\frac{p(1-p)}{n}} = \pm 1.96 \sqrt{\frac{(0.90)(0.10)}{32}} = \pm 0.10$$

- Primary Endpoint 3: Fraction of participants with MADRS scores available at all specified time points
 - If we assume that 95% of participants will have scores available at all specified time points, then $n = 32$ patients will allow this proportion to be measured with a 95% confidence interval width of $\pm 7\%$:

$$95\%CI = \pm 1.96 \sqrt{\frac{p(1-p)}{n}} = \pm 1.96 \sqrt{\frac{(0.95)(0.05)}{32}} = \pm 0.07$$

This sample size does not provide power to test the secondary endpoints for superiority. However, the observed values will be used to determine effect sizes, as well as standard deviations for the observed values. These quantities will inform the sample size calculation for the full-scale clinical trial. A minimum of 24-30 patients has previously been recommended for estimating effects sizes,^{61,62} so this feasibility trial should be large enough to provide the necessary estimates.

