9.4.4 SAFETY ANALYSES

Psychotomimetic Symptoms:

The BPRS four-item positive symptom subscale score and the CADSS-6 score will be calculated for each patient. The distribution of scores will be assessed for normality using visual analysis of histograms and using the Kolmogorov-Smirnov test. If the scores are normally distributed, then the mean score in the two groups will be compared using a two-sample t-test. If the scores are not normally distributed, then the median score in the two groups will be compared using a Wilcoxon rank sum test.

Clinical and Adverse Events Checklist:

The number of patients reporting each side effect during the study medication infusion will be determined. The incidence of each side effect will be compared between the two groups using a chi-square test (or using a Fisher exact test in the case of rare side effects).

Significant Hypertension during Infusion:

The number of patients experiencing a systolic blood pressure > 180 mmHg during the study medication infusion or receiving an antihypertensive medication during the infusion that is not on the patient's home medication list will be determined. The incidence of significant hypertension will be compared between the two groups using a chi-square test.

Tachycardia during Infusion:

The number of patients experiencing a heart rate > 100 beats per minute during the study medication infusion will be determined. The incidence of tachycardia will be compared between the two groups using a chi-square test.

Nausea and Vomiting:

The number of patients reporting nausea and vomiting will be determined. The incidence of nausea and vomiting will be compared between the two groups using a chi-square test.

Other adverse events will be coded and reported as described in section 8.3.

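### Section 9.4.1 gives a significance verdict to seven or more unadjusted between-arm tests, while the plan specifies no confidence interval for any between-arm difference

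*Combined protocol and SAP*

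**What the plan says.** Section 9.4.1 sets one rule for the whole analysis: "All inferential tests will be two-tailed, and p-values < 0.05 will be considered statistically significant".

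The tests under that rule are these:

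- Section 9.4.3: MADRS change to post-infusion day 4, and delta sleep ratio, each by t-test or Wilcoxon rank sum test.
- Section 9.4.4: the BPRS subscale and the CADSS-6, each by t-test or Wilcoxon; hypertension, tachycardia, and nausea and vomiting, each by chi-square test.
- Section 9.4.4, for the adverse events checklist: "The incidence of each side effect will be compared between the two groups using a chi-square test", with Fisher's exact test for rare effects.

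On purpose and power, section 9.1 says of the primary endpoints: "The primary endpoints of this trial will be descriptive outcomes measuring feasibility rather than hypothesis-driven efficacy outcomes". On the two secondary hypotheses it says: "This feasibility trial is intended to provide estimates of effect sizes, but it will not be powered to test these hypotheses". Section 9.2 repeats this: "This sample size does not provide power to test the secondary endpoints for superiority". Section 9.1 nevertheless frames the secondary endpoints as two-sided superiority comparisons with formal null and alternative hypotheses.

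Section 9.4.2 specifies 95% confidence intervals for the three feasibility proportions. Sections 9.4.3 and 9.4.4 specify none.

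**The concern.** The plan's stated aim and its reporting rule do not match. The secondary objectives in sections 1.1 and 3 ask for effect sizes. The analysis sections deliver a test and a verdict for each comparison, and no measure of how uncertain the difference is. Section 9.2 says effect sizes and standard deviations will be determined from the observed values, but it attaches no interval to them.

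Two things are at stake. First, a report that follows section 9.4.1 as written may call an efficacy or safety difference statistically significant without telling the reader that it came from a set of unadjusted tests. Second, and more important in a trial of this size, a safety comparison that misses p < 0.05 can be mistaken for evidence of no difference. Nothing in section 9.4.4 guards against that reading, and no interval is given that would show how large a harm remains compatible with the data.

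**Working it through.** **The plan's own figures.** Section 9.2 justifies the size by precision: "The sample size of 32 has been selected to allow the primary descriptive endpoints to be measured with acceptable levels of precision". The half-width is 1.96 × √(p(1−p)/32):

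- p = 0.25: 0.150 (stated 0.15)
- p = 0.90: 0.104 (stated 0.10)
- p = 0.95: 0.0755 (stated 0.07; it rounds to 0.08, which does not affect this point)

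The documents give no power figure and no overall error rate for the between-arm tests.

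**Inputs for the check.** Total 32 (section 9.2). Allocation, from section 6.3: "Patients will be randomized in a 1:1 ratio to ketamine or normal saline placebo". That gives 32/2 = 16 per arm, assuming no missing data. Two-sided 0.05 per test (section 9.4.1). Seven named tests (sections 9.4.3 and 9.4.4). Baseline comparisons are not tested (section 9.4.5) and there are no interim looks (section 9.4.6), so neither adds to the count.

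**Chance of at least one false positive, all nulls true.** For k independent tests it is 1 − 0.95^k:

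- k = 2 (the two efficacy tests): 1 − 0.9025 = 9.75%
- k = 7: 1 − 0.698 = 30.2%
- k = 8 (nausea and vomiting tested separately): 33.7%
- k = 13: 48.7%; k = 14: 51.2%

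With a common correlation of 0.3, simulation gives about 27% for seven tests.

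The real size of an uncorrected chi-square test at 16 v 16, by exact enumeration, is 2.8%, 5.3% and 5.7% for event rates of 10%, 20% and 30%. With four tests at 5% and three chi-square tests, 1 − 0.95⁴ × (1 − size)³ gives 25%, 31% and 32%.

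The number of checklist items is not in the documents. Assuming 5 to 20 items, all tested by Fisher's exact test (size 0.7% to 1.8% at these rates), the overall figure is 28% to 53%. Section 9.4.4 uses Fisher only for rare effects, so this range is illustrative.

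**Power of the safety tests at 16 per arm.** This is the sum, over all pairs of event counts giving p < 0.05, of the product of the two binomial probabilities. The rates are illustrative:

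| True rates | Chi-square | Fisher |
|---|---|---|
| 10% v 30% | 30% | 17% |
| 20% v 40% | 25% | 13% |
| 10% v 50% | 76% | 58% |

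A 20-point excess would therefore be missed in roughly 70% to 87% of such trials.

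**What intervals would show.** For a mean difference, the 95% half-width is t(0.975, 30) × √(2/16) = 2.042 × 0.354 = 0.72 SD. For zero events in 16, the two-sided exact 95% upper limit is 1 − 0.025^(1/16) = 20.6%.

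**The case against.** The strongest reply is that the plan already limits what can be concluded. The primary endpoints are descriptive and have intervals, lack of power for the secondary endpoints is stated twice, baseline comparisons are not tested, and no progression rule or confirmatory claim rests on any of these p-values. Section 9.4.4 also requires patient counts for each named harm, and section 10.1.6 provides an independent safety monitor. All of this stands, and it limits the seriousness of the point. It does not supply the missing intervals or qualify the rule in section 9.4.1.

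Several stronger readings are tempting, and the documents do not support them:

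- *A false positive is likely.* About 30% is substantial but not more likely than not. Passing 50% takes 14 independent tests at the full 5%, and the checklist length is unknown. The figure also assumes that every null is true. Five of the seven tests concern effects that section 2.3.1 lists as ketamine risks, so a significant result there need not be false, although that section also says that such low doses have not been linked to clinically significant changes in blood pressure or heart rate.
- *The significance label will inflate the effect size used to plan the full-scale trial.* Section 9.2 uses the observed values whatever the p-value, so no significance filter acts on the planning figure.
- *Section 9.1 declares the whole trial unpowered.* It speaks only of the two secondary hypotheses. The low power for safety is calculated here, not stated in the plan.
- *Section 9.4.9 adds further tests.* It names pain and lengths of stay as exploratory but specifies no test.

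That a report would read a non-significant harm as no difference is a risk the wording leaves open. The plan does not say it will be done.

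**Conclusion.** The point holds as a mismatch between an estimation aim and a testing rule. At least seven unadjusted between-arm tests carry a p < 0.05 verdict, and no between-arm difference has a specified interval. The chance of at least one false positive is about 30% over the seven tests under independence and all nulls true; it is lower with correlation and higher with the checklist items. The safety side matters more: power of about 13% to 30% for a 20-point difference means that a non-significant result is weak evidence of no harm. These figures assume 16 per arm, complete data and illustrative event rates. The feasibility conclusions are unaffected. The change is worth making because it costs almost nothing and improves what can be said about both efficacy and harm.

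**What to change.** - **Sections 9.4.1, 9.4.3 and 9.4.4:** report every between-arm comparison as an estimated difference with a 95% confidence interval. State that any p-values are nominal, unadjusted and exploratory.
- **Section 9.4.4:** add that a non-significant safety comparison will not be read as absence of harm.
- **Section 9.1:** reframe the two secondary endpoints as estimation rather than superiority tests. Without this, the revised analysis sections would contradict the formal hypotheses there.

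Banning the word significant altogether is not needed. Formal adjustment would be a poorer remedy. Bonferroni over seven tests sets 0.05/7 = 0.0071 per test. For an illustrative standardised difference of 0.5, where 0.5 × √(16/2) = 1.41, the normal-approximation power falls from about 29% (critical value 1.96) to about 10% (critical value 2.69).

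The cost is wording in four sections, with no new data, visits or patients. The trial gives up a formal significance claim on secondary or safety outcomes. For the secondary outcomes, the plan already says it lacks the power to test for superiority.

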9.4.2 ANALYSIS OF THE PRIMARY EFFICACY ENDPOINT(S)

Primary Endpoint 1:

The fraction of approached patients who enroll in the trial will be described using a proportion. A 95% confidence interval will be used to present uncertainty around this proportion.

The numerator will include all participants who are randomized to receive either ketamine or the placebo.

The denominator will include all patients who are approached by the research team to evaluate eligibility and offer consent. This will include patients approached by telephone in advance of their CPAP appointment, patients approached in person at CPAP, and patients approached in person in the hospital prior to the day of surgery.

Primary Endpoint 2:

The fraction of randomized participants who complete the study medication infusion will be described using a proportion. A 95% confidence interval will be used to present uncertainty around this proportion.

The numerator will include all participants who receive the study medication for at least 7 of the planned 8 hours (if enrolled under protocol version 1) or for at least 2 of the planned 3 hours (if enrolled under protocol version 2). If the study medication is temporarily halted but later restarted, the participant will still be included in the numerator if the total time with an active infusion is above the threshold defined above.

The denominator will include all participants who are randomized to receive either ketamine or the placebo.

Primary Endpoint 3:

The fraction of participants with MADRS scores available at all the specified time points will be described using a proportion. A 95% confidence interval will be used to present uncertainty around this proportion.

The numerator will include all participants with MADRS scores documented at all of the following time points: preoperative baseline, post-infusion days 1, 2, 4, 7, and 14.

The denominator will include all participants who are randomized to receive either ketamine or the placebo.

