3 OBJECTIVES AND ENDPOINTS

OBJECTIVES	ENDPOINTS	JUSTIFICATION FOR ENDPOINTS
Primary		
To evaluate the feasibility of recruiting participants to the randomized trial.	Fraction of patients approached who enroll and are randomized.	This endpoint provides an evaluation of how long it would take to

OBJECTIVES	ENDPOINTS	JUSTIFICATION FOR ENDPOINTS
		complete enrollment in a full-scale clinical trial.
To evaluate the feasibility of delivering the study medication.	Fraction of randomized patients who complete the study medication infusion.	This endpoint provides an evaluation of whether infusions were missed for logistical reasons and whether infusions were stopped early due to side effects.
To evaluate the feasibility of collecting participant outcomes.	Fraction of randomized patients with Montgomery-Asberg Depression Rating Scale (MADRS) scores available at all specified time points.	This endpoint provides an evaluation of whether the primary outcome for the full-scale clinical trial can be measured.
Secondary		
To estimate the effect size for the difference in postoperative depressive symptoms between patients receiving ketamine and patients receiving placebo.	Change in MADRS score between the preoperative assessment and post-infusion day 4	The MADRS is a reliable, valid measurement tool for depressive symptoms.
To estimate the effect size for the difference in delta sleep ratio between the intervention and control groups.	Delta sleep ratio on EEG obtained on post-infusion night 1	The delta sleep ratio, defined as the ratio between 1-4 Hz SWA during the first and second non-rapid eye movement epochs during sleep, has previously been associated with ketamine responsiveness.

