9.4.7 SUB-GROUP ANALYSES

The primary feasibility endpoints will also be assessed in sub-groups corresponding to surgical service (e.g., neurosurgery, cardiac surgery, etc.).

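### Primary Endpoint 2 is meant in part to show side-effect stopping, but completion, halts, rate reductions and RASS are never reported by arm, so the pooled figure halves any ketamine excess

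*Combined protocol and SAP*

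**What the plan says.** Section 3 gives Primary Endpoint 2 two purposes. It is to show "whether infusions were missed for logistical reasons and whether infusions were stopped early due to side effects".

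Section 9.3 sets the population: "Primary Endpoints 2 and 3 will be analyzed in an intention-to-treat population that includes all patients who are randomized". Section 9.4.2 sets the analysis: "The fraction of randomized participants who complete the study medication infusion will be described using a proportion", with a 95% confidence interval. On the denominator it says: "The denominator will include all participants who are randomized to receive either ketamine or the placebo". The numerator threshold is 7 of 8 hours under protocol version 1 and 2 of 3 hours under version 2. An infusion that was halted and restarted still counts if total active time reaches the threshold.

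Section 9.4.7 plans one breakdown: "The primary feasibility endpoints will also be assessed in sub-groups corresponding to surgical service". Treatment arm is not listed.

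Section 9.4.4 compares the arms on psychotomimetic scores, checklist side effects, significant hypertension, tachycardia, and nausea and vomiting. On the checklist it says: "The number of patients reporting each side effect during the study medication infusion will be determined". It names no analysis of infusion completion, halts, rate reductions or RASS.

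Two other provisions bear on the point. Section 7.1 sets out halting and stepwise rate reduction for sedation, and has the principal investigator consider changing the dosing once three patients have needed a halt. Section 10.1.6 has an independent safety monitor review level of sedation, among other safety data, every six months.

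**The concern.** The two purposes need different denominators. Logistical failures should be much the same in both arms, because the blinded bags are prepared and delivered in the same way, so pooling makes sense there. Stopping because of drug side effects is mainly a matter for the ketamine arm, and with 1:1 allocation about half of the pooled denominator receives saline.

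A single pooled percentage therefore cannot separate the two purposes, and it shrinks whatever difference between the arms exists. The numerator adds to this: a patient whose loading dose was abandoned, or whose rate was reduced after a halt, can still count as complete. At stake is whether this feasibility trial reports how often the ketamine infusion was interrupted, slowed or abandoned compared with saline. Designers of a full-scale trial would want that result, and Section 3 says this endpoint should supply it.

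**Working it through.** **Inputs**
- Total n = 32 (5.5 and 9.2) and 1:1 allocation (6.3), so about 16 per arm.
- Assumed completion 90%, arms pooled (9.2). No arm-specific rates are given.
- Assumption: saline completion lies between 90% and 100%. The documents do not state it.

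**1. The plan's own precision figure**

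Half-width = 1.96 × √(p(1−p)/n) = 1.96 × √(0.90 × 0.10/32) = 0.104. This agrees with the ±0.10 in 9.2, which is not in dispute.

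**2. Size of the dilution**

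Let q_K and q_S be the non-completion rates on ketamine and saline. Under 1:1 allocation the pooled rate is (q_K + q_S)/2. Its excess over saline is (q_K + q_S)/2 − q_S = (q_K − q_S)/2, which is half of the true excess.

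Pooled completion for a given ketamine rate:

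| Ketamine completion | Pooled, saline 100% | Pooled, saline 90% |
|---|---|---|
| 90% | 95% | 90% |
| 80% | 90% | 85% |
| 70% | 85% | 80% |
| 60% | 80% | 75% |

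Read the other way, a pooled 90% fits any ketamine completion from 80% (saline 100%) to 90% (saline 90%).

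**3. Illustration with counts** (16 per arm, 16/16 saline infusions completed, exact Clopper-Pearson 95% intervals)

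| Ketamine arm | Reported pooled |
|---|---|
| 13/16 = 81% (54% to 96%) | 29/32 = 91% (75% to 98%) |
| 12/16 = 75% (48% to 93%) | 28/32 = 88% (71% to 96%) |

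**4. Precision of a by-arm estimate**

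At n = 16 and 90% completion, the half-width is 1.96 × √(0.09/16) = 0.147, against 0.104 pooled. At 80% it is 1.96 × √(0.16/16) = 0.196.

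For 3/16 against 0/16 non-completers, the two-sided Fisher p-value is 2 × C(16,3)/C(32,3) = 2 × 560/4960 = 0.23. The contrast is descriptive only.

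**5. How far the halt trigger in 7.1 helps**

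Suppose only ketamine patients are halted. The chance that 16 of them produce at least three halts is 21% if each has a 10% risk, 65% at 20% and 90% at 30%. The trigger would often respond to a marked problem, but it counts halts in both arms together and produces no reported comparison.

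**6. What "completed" covers**

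The threshold is 2/3 = 67% of planned time under version 2 and 7/8 = 87.5% under version 1. The rate is not part of the definition, so an infusion run at a reduced rate can count as complete. Completion by arm is therefore not enough without counts of halts and rate reductions.

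**The case against.** The strongest reply is that the stated objective is delivery of the study medication, which in a double-blind trial means both kinds of bag. On that reading, one intention-to-treat proportion is the right primary estimate. This stands. A reader might infer that the pooled denominator is an error, but the documents do not support that. What is missing is a second tabulation for the other stated purpose.

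A reader might also infer that 29/32 would be declared a success. The documents set no progression or success threshold for this endpoint. The 90% in 9.2 is a planning assumption for precision, so matching it triggers no decision.

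Nor is tolerability left unexamined. Section 9.4.4 compares several side effects by arm, 7.1 has the three-patient trigger, 10.1.6 has the sedation review, and other adverse events are reported under 8.3. In the 13/16 illustration, three early stops that were halts would meet the trigger. The checklist's items are not in the documents, so drowsiness may already be compared by arm. These provisions reduce the gap, but none commits the trial to reporting completion, halts, rate reductions or RASS by arm.

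It would also go too far to treat sedation as the only reason for a halt: 7.1 allows halts for other reasons after discussion with the principal investigator.

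Finally, a by-arm split has limits. Sixteen per arm is few, and the arms may mix the 8-hour and 3-hour regimens in numbers that are not stated. Both are reasons to present the split descriptively and by version. Neither is a reason to omit it.

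**Conclusion.** The point holds as a gap between a stated purpose and the planned reporting. One of the two questions that Section 3 assigns to Primary Endpoint 2 has no planned answer, because completion is reported only over both arms and nothing in 9.4.4 or 9.4.7 gives completion, halts, rate reductions or RASS by arm.

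The factor of one half follows from 1:1 allocation alone. The absolute size depends on saline completion, which must be assumed: with 90% to 100%, a ketamine rate of 70% would appear as 80% to 85%. The counts with 16 per arm are illustrations and not predictions.

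The change is worth making because it affects what the trial can report about the ketamine infusion. It alters no planned decision rule, and the pooled estimate and its ±0.10 remain correct for what they measure.

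**What to change.** - **Section 9.4.2, Primary Endpoint 2.** Keep the pooled proportion as the primary estimate. Add completion by randomised arm with an exact 95% interval for each arm, and the difference between arms with a 95% interval. Show these by protocol version, since the planned duration and threshold differ.
- **Section 9.4.4.** Add by arm: the number with any halt, the number with a rate reduction, the number permanently stopped (with reason where recorded), and the lowest documented RASS during the infusion. State that these are descriptive.

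**Cost.** The change is plan wording and a few table rows, with no effect on sample size or conduct. Administration is documented in the electronic record (6.4), and RASS is assessed by the bedside nurse with one extra check after the loading dose (8.2). Two limits should be stated. The documents do not show that the reason for stopping an infusion is captured (7.2 covers reasons for leaving the study), so one CRF field may be needed. The lowest RASS also depends on how often nurses assess it, which is left to unit practice. By-arm intervals will be wide, about ±0.15 instead of ±0.10 at 90% completion, and wider still within a protocol version.
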